## 8. RESEARCH METHODS

### 8.1. Study Design

- **Retrospective analysis** of patients with AS that received etanercept from Baghdad teaching hospital (Rheumatology center) from August 2012 until March 2020 (inclusion and exclusion criteria will apply for selecting patients).
- **Primary objective:** determine the clinical impact of early referral for management in patients with AS compared to delayed management.
- **Secondary objective:** determine the influence of early referral on the response to biological treatment.

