### **8.3. Data Sources**

Patients will be identified from the rheumatology patient registry with rheumatoid arthritis and will obtain information on patient demographics (age, gender), education level (years), present smoking status, disease duration (years), current steroid therapy (yes/no), baseline bath ankylosing spondylitis disease activity index (BASDAI), Bath Ankylosing spondylitis functional index (BASFI), human leukocyte antigen B27 (HLA-B27), anticitrullinated protein antibody (anti-CCP) status.

Primary Outcomes: Disease activity Index BASFI and BASDAI from the last follow-up visit.

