### **8.6. Data Analysis**

All covariates will be summarized to get information about frequency distribution and mean, median or standard deviation. Numbers and percentages will be provided for categorical variables when performing descriptive analysis. Means, medians, standard deviations, or interquartile range as appropriate will be provided for continuous variables when performing descriptive analysis of continuous data.

Patients will be divided according to the mean of disease duration groups (below and above mean) and unadjusted comparisons between groups of the covariates and they will be evaluated using appropriate tests: chi-squared test will be used for categorical variables, t-test will be used for continuous variables, and the Kruskal-Wallis test for non-parametric variables; p-values will be generated.

We will determine the effect of early referral on the biologic treatment response patients with AS a multivariate analysis by using a stepwise linear regression model. The response variable is defined as BASFI and BASDAI at last visit. The baseline variables are considered demographic data, disease duration (years), methotrexate (yes/no), Current steroid therapy (yes/no), baseline BASFI, BASDAI, HLA-B27 positive (yes/no), anti-CCP (yes/no), present smoking (yes/no).

We will determine the effect of early response by using the difference in change between the baseline of BASDAI and BASFI and last follow-up. P-value <0.05 will be considered statistically significant.

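### The change-from-baseline comparison states no adjustment for the starting score, baseline enters the last-visit regression only through stepwise selection, and the two can disagree

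*Combined protocol and SAP*

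**What the plan says.** Section 8.6 contains two analyses that bear on response.

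- **Last-visit regression.** The effect of early referral on response is to be assessed by a "multivariate analysis by using a stepwise linear regression model". Its outcome is explicit: "The response variable is defined as BASFI and BASDAI at last visit". The candidate variables include disease duration in years and "baseline BASFI, BASDAI, HLA-B27 positive (yes/no), anti-CCP (yes/no), present smoking (yes/no"). Nothing says that any of them is kept regardless of the selection procedure.
- **Change comparison.** A separate closing paragraph reads: "We will determine the effect of early response by using the difference in change between the baseline of BASDAI and BASFI and last follow-up". It names no model, covariate or test. The next sentence is "P-value <0.05 will be considered statistically significant".

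The groups are formed after the fact: "Patients will be divided according to the mean of disease duration groups (below and above mean").

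Section 8.3 settles which outcome is primary: "Primary Outcomes: Disease activity Index BASFI and BASDAI from the last follow-up visit". Section 8.1 adds a secondary objective, to "determine the influence of early referral on the response to biological treatment", without naming an endpoint for it. The null hypothesis in Section 8.2 is also framed in terms of response. No section says how the change comparison relates to the regression, or which one carries the conclusion on response if they differ.

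**The concern.** Change from baseline depends on where a patient starts. When baseline and follow-up are imperfectly correlated, patients with high scores tend to fall further, whatever group they belong to. Randomisation would balance this on average. A split at mean disease duration does not.

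The only two-group tests named outside the regression are unadjusted ones, and the change sentence is followed by a significance rule. An unadjusted test of change is therefore a natural reading, and the text leaves the analyst free to run it. If one group starts worse, that test can declare a difference in response that disappears once starting severity is taken into account. The last-visit regression would be the safeguard, but stepwise selection may drop the baseline score, or disease duration itself.

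At stake is the study's central statement on whether early patients respond differently. The secondary objective has no named endpoint, so the change result could readily be reported as its answer.

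**Working it through.** The plan states no sample size (Section 8.4), SD, correlation or expected difference, so it has no figure to reproduce. What follows is an illustration.

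**Inputs from the plan:** non-randomised groups; change and last-visit score both analysed; significance at p<0.05 (sidedness not stated, two-sided assumed).

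**Assumed inputs, not in the documents:** SD 2 at both visits; baseline-to-follow-up correlation r = 0.3, 0.5 or 0.7; baseline gap d = 0, 0.5 or 1 point; 50, 100 or 200 per group; no group effect given baseline.

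**Formulas**, as worse-starting group minus the other (lower score is better):

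- Expected difference in change = (r − 1)d
- Expected unadjusted difference at last visit = r·d
- Expected baseline-adjusted difference = 0
- SD of change = 2·√(2(1 − r))
- SE of the difference in change = SD of change × √(2/n)
- Rejection probability ≈ Φ(|difference|/SE − 1.96), with a negligible second tail when d = 1

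**Results for d = 1 and 100 per group:**

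| r | Difference in change | Unadjusted last-visit difference | SD of change | SE | Ratio | Change test rejects: formula (simulated) | Baseline-adjusted test rejects: simulated |
|---|---|---|---|---|---|---|---|
| 0.3 | −0.7 | +0.3 | 2.366 | 0.335 | 2.09 | 55% (54%) | 4.9% |
| 0.5 | −0.5 | +0.5 | 2.000 | 0.283 | 1.77 | 42% (41%) | 5.4% |
| 0.7 | −0.3 | +0.7 | 1.549 | 0.219 | 1.37 | 28% (28%) | 4.1% |

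Simulations used 3,000 runs per scenario.

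**Sensitivity to the assumptions:**

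- 1-point gap, 50 to 200 per group: the change test rejects in 16% to 84%.
- 0.5-point gap, same sizes: 8% to 32%.
- No gap: 5%.
- The baseline-adjusted test rejects in 4.1% to 5.4% across all nine combinations of d and r at 100 per group.

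**Why common adjustment removes the disagreement.** Change equals last-visit score minus baseline score. Take the same patients, covariates and group term, with baseline in the model. Regressing change instead of last-visit score lowers the baseline coefficient by exactly 1 and leaves the group coefficient and its standard error unchanged.

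**The same setup under a different null.** Suppose instead that both groups have equal true mean change. Unadjusted change then rejects at its nominal rate (4% to 5% simulated). The adjusted difference is (1 − r)d, which is 0.7 or 0.5 for r = 0.3 or 0.5 with a 1-point gap. Its SE is 2·√(1 − r²) × √(2/n) × √(1 + d²/16). At 100 per group this is 0.278 or 0.252, the ratios are 2.52 and 1.98, and rejection is about 71% and 51% (simulated 72% and 50%). The two analyses answer different questions when baselines differ.

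**The case against.** The strongest reply is that the plan already has a baseline-adjusted response analysis. Sections 8.3 and 8.6 make the last-visit score the primary outcome and the defined response variable, and baseline scores are candidates in that regression. A reader might infer that raw change is the plan's response endpoint; the documents do not support that. Stepwise selection would also usually keep a useful baseline score: in simulations with r = 0.3 to 0.5 and 50 to 100 per group, baseline alone reached p<0.05 in 87% to 100% of studies. This stands, and it narrows the point. It does not guarantee retention alongside the other candidates, and it says nothing about the change comparison.

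A reader might also infer that the two planned analyses will point in opposite directions, as the change and unadjusted last-visit columns above do. The plan does not pair those two. If the regression keeps baseline, the expected conflict under the assumed null is between a non-zero change difference and an adjusted estimate near zero.

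Third, calling unadjusted change biased presupposes that the target is the effect given baseline. Under an equal-change null, the adjusted analysis is the one that rejects too often. Disease duration also precedes the baseline score, so baseline may carry part of the effect of early referral. This stands as well: adjustment is a choice of question and has to be declared as one. It is, however, the choice the plan already leans towards by listing baseline scores in its response regression.

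Finally, the absence of adjustment is read from silence, since the sentence does not even name the groups. That makes it an incomplete specification, not a stated decision to leave change unadjusted.

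**Conclusion.** The point holds in limited form. The change comparison has no stated adjustment for the starting score, the last-visit regression does not secure that adjustment, and nothing says how the two results are to be reconciled on response.

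The size is conditional. With SD 2, r = 0.3 to 0.7, a 1-point gap, 100 per group and no effect given baseline, an unadjusted change test rejects in about 28% to 55% of studies, with 0.3 to 0.7 points of apparent extra improvement in the worse-starting group. With equal baselines it rejects in 5%.

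A reader might infer that the delayed group starts worse and would be flattered by the change analysis. The documents give neither the direction nor the size of any baseline gap, so this is a risk to guard against and not a demonstrated bias.

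**What to change.** Amend Section 8.6 as follows:

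1. Estimate the group effect on change in BASDAI from a linear model with the early/delayed term and baseline BASDAI forced in. Do the same for BASFI with baseline BASFI.
2. In the last-visit regression, exempt the same instrument's baseline score and the early/delayed (disease duration) term from stepwise selection.
3. Use the same covariates, and the same form of the disease-duration term, in both models. Change and last-visit score then give the same group estimate.
4. Report raw mean changes by group descriptively, without a p-value.
5. State that the estimate is conditional on baseline severity, that in non-randomised groups it can differ from an unadjusted comparison of change, and that it does not remove other confounding.

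The cost is a few sentences. Baseline BASDAI and BASFI are already extracted under Section 8.3, so no new data are needed. Section 5 puts the end of data collection at 1 October 2020, before this version's date of 29 July 2021, so the amendment should say whether results were already known when it was made.

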### **8.7. Quality Control**

Not Applicable (N/A).

### **8.8. Limitations of the Research Methods**

Missing data that could lead to bias is a limitation in this study.

### **8.9. Other Aspects**

Not Applicable (N/A).

## **9. PROTECTION OF HUMAN SUBJECTS**

### **9.1. Patient Information**

This study involves data that exist in anonymized structured format and contain no patient personal information.

### **9.2. Patient Consent**

As this study involves anonymized structured data, which according to applicable legal requirements do not contain data subject to privacy laws, obtaining informed consent from patients by Pfizer is not required.

### **9.3. Institutional Review Board (IRB)/Independent Ethics Committee (IEC)**

Not required.

### **9.4. Ethical Conduct of the Study**

The study will be conducted in accordance with legal and regulatory requirements, as well as, with scientific purpose, value, and rigor, and follow generally accepted research practices described in the Guidelines for Good Pharmacoepidemiology Practices (GPP) issued by the International Society for Pharmacoepidemiology (ISPE), Good Epidemiological Practice (GEP) guidelines issued by the International Epidemiological Association (IEA), and Good Practices for Outcomes Research issued by the International Society for Pharmacoeconomics and Outcomes Research (ISPOR).

## **10. MANAGEMENT AND REPORTING OF ADVERSE EVENTS/ADVERSE REACTIONS**

[figure not shown]
This study involves data that exist as structured data by the time of study start.

In these data sources, individual patient data are not retrieved or validated, and it is not possible to link (ie, identify a potential association between) a particular product and medical event for any individual. Thus, the minimum criteria for reporting an adverse event (AE) (ie, identifiable patient, identifiable reporter, a suspect product, and event) cannot be met.

## **11. PLANS FOR DISSEMINATING AND COMMUNICATING STUDY RESULTS**

In the event of any prohibition or restriction imposed (eg, clinical hold) by an applicable competent authority in any area of the world, or if the investigator is aware of any new information which might influence the evaluation of the benefits and risks of a Pfizer product, Pfizer should be informed immediately.

[figure not shown]
PFIZER CONFIDENTIAL

**13. LIST OF TABLES**

Not Applicable (N/A).

[figure not shown]
**14. LIST OF FIGURES**

Not Applicable (N/A).

**ANNEX 1. LIST OF STAND-ALONE DOCUMENTS**

None.

PFIZER CONFIDENTIAL

